CRF	Case report form
CTCAE	Common Terminology Criteria for Adverse Events
CTRL	Clinical and Translational Research Laboratory
DSMC	Data and Safety Monitoring Committee
ECOG	Eastern Cooperative Oncology Group
EGFR	Epidermal growth factor receptor
EIAED	Enzyme-inducing antiepileptic drug
GBM	Glioblastoma
HDAC	Histone deacetylase
Hgb	Hemoglobin
IHC	Immunohistochemistry
IRB	Institutional Review Board
LLN	Lower limit of normal
MCC	Massey Cancer Center
NO	Nitric oxide
PDE5	Phosphodiesterase type 5
PDGFR	Platelet-derived growth factor receptor
PFS	Progression-free survival
PI3	Phosphoinositide 3
PRMC	Protocol Review and Monitoring Committee
RANO	Response Assessment in Neuro-Oncology
SAE	Serious adverse event
UP	Unanticipated problem
VCU	Virginia Commonwealth University
VEGFR	Vascular endothelial growth factor receptor
WBC	White blood cell count
WNL	Within normal limits

1 BACKGROUND

1.1 Recurrent or Progressive High-Grade Glioma

High-grade gliomas are the most common malignant primary brain tumors in adults (2) and are associated with poor prognosis. Despite optimal therapy, nearly all high-grade gliomas eventually recur. The median survival following recurrence is only 25 to 30 weeks for World Health Organization (WHO) grade IV gliomas and 39 to 47 weeks for WHO grade III gliomas (3, 4). GBMs account for approximately 60% to 70% of high-grade gliomas. Anaplastic astrocytomas comprise 10% to 15%. Anaplastic oligodendrogliomas and anaplastic oligoastrocytomas combined represent 10% of high-grade gliomas. Less common tumors such as anaplastic ependymomas and anaplastic gangliogliomas make up the rest (5).

Many targeted agents against these aberrant pathways or affecting glioma stem cell growth are under investigation in recurrent high-grade glioma. Bevacizumab (Avastin; Genentech, South San Francisco, CA), a monoclonal antibody against VEGF, has been studied extensively in this patient population. In a randomized, multicenter, noncomparative phase 2 trial, the estimated 6-month progression-free survival (PFS) rates for patients with recurrent GBM were 42.6% for bevacizumab alone and 50.3% for bevacizumab plus irinotecan (6). Additional therapies are urgently needed.

1.2 Sorafenib

Sorafenib is a multi-targeted protein kinase inhibitor that was originally developed as an inhibitor of RAF-1, a component of the ERK1/2 pathway. Sorafenib was subsequently shown to inhibit multiple other kinases, including class III tyrosine kinase receptors such as platelet-derived growth factor receptors (PDGFRs), vascular endothelial growth factor receptors (VEGFRs), c-Kit, and FLT3. VCU investigator [name] and collaborators have shown *in vitro* that sorafenib, through its effects on the PDGFRs, can activate Src non-receptor tyrosine kinases, and that this effect plays a role in the activation of death receptors resulting in tumor cell death (7, 8). Lethality of sorafenib in cancer cells is enhanced by concomitant histone deacetylase (HDAC) inhibitor exposure (9, 10). Cell death is through the extrinsic pathway of apoptosis.

In the USA, sorafenib is approved for the treatment of differentiated thyroid carcinoma refractory to radioactive iodine treatment, and renal cell and hepatocellular carcinomas.

Ongoing studies in GBM have investigated sorafenib as a single agent and in combination with mTOR inhibitors, epidermal growth factor receptor (EGFR) inhibitors, and bevacizumab. To date, there are no studies combining sorafenib with HDAC inhibitors in high-grade glioma.

1.3 Valproic Acid

Valproic acid (sodium valproate, valproate) is an anti-seizure medication in common medical use, and is referred to as a non-enzyme-inducing antiepileptic drug (non-EIAED). It is frequently used in chemotherapy regimens due to the fact that it does not modulate the cytochrome p450 system; thus, valproic acid does not have many of the drug-drug interactions with standard chemotherapy agents that are common for other antiepileptic drugs. It has subsequently been shown that valproic acid also acts as a HDAC inhibitor

(11). Valproic acid has been demonstrated at clinically relevant concentrations to inhibit class I (HDAC 1, 2, and 3, along with HDAC 8) and class II, subclass I HDACs (HDAC 4,5, and 7) (11).

HDAC inhibitors are a class of drugs that inhibit the enzymes that deacetylate histones (12). By regulating histone acetylation, chromatin condensation is changed and the levels of transcription may be altered. Many other proteins, including those that are cytosolic, are also acetylated and it is probable that the actions of HDAC inhibitors involve both the regulation of gene expression (eg, FAS-ligand), as well as regulating acetylation of other cytosolic proteins (eg, HSP90) (13). In previously published work in GI tumor cells by [name] and colleagues, HDAC inhibitors were shown to increase the levels of FAS-ligand, as well as its receptor CD95, both of which played a role in HDAC inhibitor toxicity (7, 8). His group has more recently demonstrated that knockdown of CD95 protected CNS tumor cells from the combination of sorafenib and valproic acid (14).

Valproic acid in combination with temozolomide and radiotherapy is currently under investigation in the treatment of newly diagnosed GBM. There are over 10 studies, ongoing or recently completed, that have evaluated HDAC inhibitors in the treatment of CNS tumors, none of which are combined with sorafenib.

1.4 Sildenafil

Sildenafil is FDA approved for the treatment of both erectile dysfunction and pulmonary hypertension, and has been administered to men, women, and children on a chronic daily basis.

Intracellular cyclic guanosine monophosphate (cGMP) levels reflect the balance of synthesis by guanylate cyclases and degradation by phosphodiesterases. Nitric oxide (NO) activates guanylate cyclase in diverse tissues including vasculature, and cGMP is the second messenger that induces smooth muscle relaxation and vasodilation. Sildenafil increases intracellular cGMP and induces vasodilation. This activity is generally attributed to selective inhibition of cGMP-specific phosphodiesterase type 5 (PDE5). Sildenafil and PDE5 inhibitors may also have other functions that relate to anticancer therapy, specifically relating to blood brain barrier (BBB) interactions and drug efflux mechanisms. PDE5 inhibitors have been shown to increase chemotherapy delivery to brain tumors in animal models, through increased tumor cGMP levels (15). ATP-binding cassette (ABC) proteins transport various molecules across extra- and intracellular membranes. Sildenafil has also been shown to inhibit the ABCB1 and ABCG2 drug efflux pumps, and reverse ABCB1 and ABCG2 mediated chemotherapeutic drug resistance (16). The ABCG2 transporter has recently been shown to be the dominant transporter that limits transport of sorafenib into the brain (17). This is clinically relevant as GBM is considered to be a diffuse disease, with many areas of tumor residing in areas of the brain with an intact BBB. Inhibition of the ABCG2 transporter with sildenafil may increase sorafenib drug concentrations in the brain, improving sorafenib anti-tumor efficacy.

To date, there are no CNS tumor studies utilizing drug efflux pump modulators, like sildenafil, in conjunction with sorafenib.

1.5 Sorafenib + Valproic Acid Preclinical Data

[name] and colleagues have tested the combination of sorafenib and HDAC inhibitors in multiple GBM isolates. These studies have included: GBM cells expressing mutant active forms of the EGFR (GBM6, EGFR vIII; GBM12, mutant active full-length EGFR), GBM cells lacking PTEN function (GBM14), GBM cells expressing a mutant active phosphoinositide 3 (PI3)-kinase and PDGFR α (GBM5), or GBM cells with low levels of growth factor receptors (GBM15). There appear to be differences in drug combination sensitivity based on the molecular phenotype of the GBM cell line. Sorafenib toxicity was enhanced by valproate in the GBM6 EGFR mutant variant III cells in a dose-dependent fashion ([Figure 1](#)). This mutation in EGFR leads to a truncated EGFR that is constitutively active, but does not bind ligand. GBM15 and GBM14 were both sensitive to the drug combination, similar to GBM6 (data not shown).

In the following figures, valproic acid (VAL) was the HDAC inhibitor used in combination with sorafenib (SOR).

[figure not shown]

Figure 1. GBM6 cells were treated with vehicle or sodium valproate (1 mM). Thirty minutes later cells were treated with vehicle or sorafenib (3 μ M; 6 μ M). Cells were isolated 24 h and 48 h later. Viability was determined by trypan blue exclusion (n=3, +/- SEM) * p<0.05 greater than corresponding vehicle-control treated cells.

GBM12 full-length EGFR mutant cells appear to be more resistant to the drug combination than GBM6 truncated EGFR mutant cells ([Figure 2](#)).

[figure not shown]

Figure 2. GBM12 cells were treated with vehicle or sodium valproate (1 mM). Thirty minutes later cells were treated with vehicle or sorafenib (3 μ M; 6 μ M). Cells were isolated 48 h later. Viability was determined by trypan blue exclusion (n=3, +/- SEM) * p<0.05 greater than corresponding vehicle control treated cells.

The cells that were clearly most sensitive to the sorafenib and valproic acid drug combination were GBM5 cells; cells that express one of the growth factor receptor targets of sorafenib, PDGFR α ([Figure 3](#)).

[figure not shown]

Figure 3. GBM5 cells were treated with vehicle or sodium valproate (1 mM). Thirty minutes later cells were treated with vehicle or sorafenib (1, 2, 3, or 6 μ M). Cells were isolated 24 and 48 h later. Viability was determined by trypan blue exclusion (n = 3, +/- SEM) * p < 0.05 greater than corresponding vehicle-control treated cells.

Collectively, this data suggests that the combination of sorafenib and valproic acid is worth investigating in GBM. It appears from the preclinical data that different molecular phenotypes may have different sensitivities to the drug combination, and this will be investigated during the study.

1.6 Rationale

Promising single agent *in vitro* activities and potentially complementary mechanisms of action suggest that the combination of sorafenib, valproic acid, and sildenafil may have therapeutic potential for the treatment of high-grade glioma in the clinic. The combination of sorafenib and valproic acid is predicated on the basis that sorafenib activity is enhanced by HDAC inhibition. The addition of sildenafil is based on its ability to block ABCB1 and ABCG2 drug efflux pumps. As the ABCG2 transporter is the primary transporter involved in the efflux of sorafenib at the BBB, blocking its action is predicted to increase the concentration of sorafenib in the brain.

1.7 Clinical Considerations

One dose level of sorafenib will be tested in this phase 2 study. Sorafenib will be dosed at the FDA approved dose of 400 mg orally twice daily, which is well established as the maximum tolerated dose for continuous dosing. This dose of sorafenib has been tested in recurrent GBM in 5 separate phase 2 studies in combination with temozolomide ([18](#), [19](#)), temsirolimus ([20](#)), erlotinib ([21](#)), and bevacizumab ([22](#)).

In the study by Reardon et al ([18](#)), 12 patients were taking CYP3A EIAEDs, 10 patients were taking non-EIAEDs, and 10 patients were not taking any medication to prevent seizures (valproic acid is a non-EIAED). Overall, 4 patients (13%) required dose modification or discontinuation of sorafenib for grade 3 or 4 elevation of amylase/lipase, and 3 patients (9%) required dose modification or discontinuation of sorafenib for grade 3 PPE. Only 2 of the 4 patients with elevated amylase/lipase were symptomatic and in 1 of those 2 patients, underlying gallstones were the likely etiology. Of note, 5 out of 10 patients on the non-EIAED arm who underwent pharmacokinetic sampling required sorafenib dose interruption or modification during cycle 1 of therapy. For patients not on EIAEDs, day-28 sorafenib AUC 0-24 was significantly higher compared to day 1. This increase may also have been mildly augmented by the discontinuation of dexamethasone (a mild CYP3A inducer) in 3 patients.

In the study by Zustovich et al ([19](#)), all patients (n=43) received oxcarbazepine, a hepatic CYP3A inducer (EIAED). Grade 3-4 toxicity was observed in 4 patients (9%) with PPE, 1 patient (2%) with diarrhea and 1 patient (2%) with lipase elevation. It is possible that if these patients had been taking non-EIAEDs the toxicity ascribed to sorafenib would have been higher.

In the study by Lee et al ([20](#)), patients receiving EIAEDs were excluded. In the phase 1 component of the trial, 1/6 (17%) developed grade 3 diarrhea. In the phase 2 component of the trial, 1/19 patients (5%) developed grade 3 lipase elevation and 1/19 patients (5%) experienced grade 3 diarrhea. The frequency of these toxicities is well below the threshold of 35% that is proposed in the current study.

Similarly, in the study by Peereboom et al ([21](#)), patients receiving EIAEDs were excluded. Grade 3 or 4 events felt to be possibly, probably or definitely related to sorafenib or erlotinib ranged from 2% (elevated transaminases, PPE, diarrhea) to 7% (elevated lipase) to 9% (fatigue). The elevations of lipase were asymptomatic. The frequency of these toxicities is well below the threshold of 35% that is proposed in the current study. There were no unexpected toxicities.

In the study by Galanis et al (22), 3/19 patients (16%) experienced grade 4 non-hematologic toxicity and a 42% discontinuation rate. Fatigue (which could be ascribed to sorafenib and/or bevacizumab) and hypertension (due to bevacizumab) were the 2 most commonly observed toxicities. Decrease of the starting sorafenib dose from 200 mg twice daily to 200 mg daily resulted in improved treatment tolerance.

Unfortunately, in none of these 5 studies was notable efficacy seen. Partial response rates of 3-12%, 6-month PFS of 0-26% and overall survival of 5.6-9.6 months were reported. It is our hypothesis that the addition of valproic acid with its HDAC activity, coupled with sildenafil with its drug efflux pump inhibitory activity, could synergistically increase the likelihood of GBM tumor cell kill without concomitant unacceptable sorafenib (or valproic acid) toxicity.

Since the accepted and expected rate of grade 3+ toxicities of sorafenib alone is 35%, the safety component in this trial will focus on identifying a measurable increase in that rate of overall toxicities. The safety lead-in component of this study will serve to screen for an increase in early toxicities. The safety stopping rule will permit monitoring of both early and late toxicities, but practically speaking only becomes applicable if early toxicities are deemed not excessive. Note that grade 5 (fatal) toxicity was not seen in any of the 5 studies cited above.

If toxicity is observed that could be ascribed to sorafenib, then the sorafenib dose will be modified according to Section 7. Likewise, if toxicity is observed that could be ascribed to valproic acid, then the valproic acid dose will be modified according to Section 7, which simply follows Good Clinical Practice principles. Total and free serum valproate levels can be obtained on a same-day basis from the clinical laboratory to help guide the investigator to the appropriate dose modification. If toxicity is observed that could be ascribed to sildenafil, then the sildenafil dose will be modified according to Section 7. If sorafenib or valproic acid toxicity is observed, it is important to first modify the dose of sorafenib or valproic acid and maintain the sildenafil dose constant, since reducing the sildenafil dose may result in decreases of tumor tissue levels of both sorafenib and valproic acid, abrogating the therapeutic effect that this phase 2 trial is designed to achieve. If dose modification of sorafenib or valproic acid does not reverse drug toxicity attributable to those agents, then subsequent sildenafil dose reductions may also be needed to accomplish that goal. We believe this is a rational approach to optimize tumor cell kill while minimizing risk to study patients.

The FDA recommended initial dose of valproic acid is 10-15 mg/kg per day in divided doses; for the purposes of this study valproic acid will generally be dosed twice daily, to allow for ease of administration of all 3 agents at the same time. After initiation of therapy at 10-15 mg/kg/day, escalation of the dose over approximately 1 week to \geq lower limit of normal (LLN) will be performed. Prior research with valproic acid suggests that therapeutic concentrations of valproic acid can inhibit histone deacetylation (11, 23, 24). For patients with a seizure disorder being treated with valproic acid, serum levels should be checked 1 week after the initial dose; therapeutic concentrations are usually in the 50-150 mcg/mL range. For patients who develop neurologic deterioration, valproic acid levels will be checked to make sure that supratherapeutic drug concentrations are not the source of the neurologic deterioration.

It is generally accepted that patients with GBM and seizures should be treated with a non-EIAED to minimize CYP3A-mediated drug interactions and, more specifically, to avoid

inadvertent lowering of cytotoxic drug concentrations in GBM tumor cells. Which non-EIAED to choose is a matter of personal preference for the treating physician; there is no published practice parameter or “standard of care”. That said, there is a growing body of evidence that valproic acid is a logical first choice in this setting 1) because it is an effective AED and 2) because of its HDAC activity. Weller et al (25) showed that GBM patients receiving valproic acid appeared to derive more survival benefit from temozolomide/radiotherapy than patients receiving an EIAED or not receiving any AED. Guthrie et al (26) and Barker et al (27) came to a similar conclusion. Felix et al (28) corroborated this observation in 94 children with a variety of primary CNS tumors. Furthermore, Kerkhof et al (29) demonstrated that valproic acid monotherapy conferred equivalent freedom from seizures (78%) as did levetiracetam (70%) in patients with GBM. Therefore, we do not believe that patients in this trial will be placed at any seizure control disadvantage when treated with valproic acid and, indeed, may benefit from the associated HDAC activity directed against their tumor.

Of note, there is a single case report describing the use of sorafenib plus valproic acid in an infant with a spinal GBM (30). Marked clinical and radiographic improvement was shown, and no side effects of the combination were observed.

Sildenafil will be dosed at 50 mg orally twice daily, at the time of sorafenib dosing. The purpose of twice daily dosing is to have maximal sildenafil concentrations at the time of sorafenib dosing, to maximize inhibition of ABC transport system and to try to maximize increases in sorafenib transport across the BBB. This dosing schedule is less frequent than some dosing schedules used in pulmonary hypertension studies and heart failure studies. One study evaluating pulmonary hypertension in heart failure dosed sildenafil at 50 mg, 3 times a day, for a period of 12 months, and did not report significant toxicities (31).

There are no major overlapping toxicities relating to valproic acid, sorafenib, or sildenafil that suggest that the combination would be subject to higher rates of toxicity. There is a low incidence of diarrhea in patients treated with sorafenib that may be exacerbated with valproic acid; this will be monitored closely. There is an early stopping rule in place should there be unexpected significant toxicities from the combination. It is expected from clinical experience that a fraction of patients will not tolerate full dose sorafenib in the chronic setting, and these patients may continue therapy at reduced dose levels.

One previously published study has evaluated sorafenib in combination with sildenafil (32). This study was a non-cancer study, which treated patients with pulmonary hypertension with sorafenib and prostanoid therapy, half of whom were also on chronic sildenafil. No grade 3 or 4 drug-related toxicities were reported.

Children under the age of 18 will be excluded from study. There are no published reports regarding the safety of sorafenib at the fixed dose of 400 mg orally, twice a day, in the pediatric population, and evaluating the safety of full dose sorafenib in the pediatric population is beyond the scope of the study.

In patients with progressive high-grade glioma, survival time is generally short. Six-month PFS will be used as the primary endpoint in the study. This endpoint has been accepted by the FDA as a reasonable endpoint in recurrent or progressive GBM, and a positive 6-month PFS led to the approval of bevacizumab as second-line therapy in this disease.

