6.4.2 Qualifying Toxicities for the Safety Lead-In and Safety Stopping Rule

Qualifying toxicities for the safety lead-in are evaluated weekly during the first 4 weeks of combination treatment for each of the first 6 patients deemed evaluable for qualifying toxicity for the safety lead-in (see Section [10.1](#)).

Qualifying toxicities for the safety stopping rule are evaluated regularly during the first 4-week cycle of combination treatment for patients deemed evaluable for the early stopping rule (see Section [10.1](#)).

Qualifying toxicities are defined as any of the following that are possibly, probably, or definitely related to drug therapy:

Any grade \geq 3 toxicity, except the following:

- nausea, vomiting, or diarrhea in the absence of adequate prophylaxis and/or responsive to medical management
- grade 3 thromboembolic event

- grade 3 hyperglycemia
- grade 3 PPE (hand-foot syndrome)
- fatigue responsive to medical management
- grade 3 hypertension
- electrolyte abnormalities that, once corrected, can be maintained with oral repletion
- grade 3 anemia, platelets, neutrophils, WBC, lymphocytes, febrile neutropenia

6.4.3 See Section [8.5](#) for AE and qualifying toxicity reporting procedures.

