Pancreatitis	Discontinue valproic acid. Note: Elevations in lipase are very common in patients taking sorafenib. A diagnosis of pancreatitis should not be made solely based on abnormal laboratory values.

Valproic acid should be immediately discontinued in the presence of significant hepatic dysfunction, suspected or apparent.

Patients should be monitored for the emergence or worsening of depression, suicidal thoughts or behavior, and/or unusual changes in mood or behavior.

Significant bleeding or coagulopathy is an indication for reduction of the dosage or discontinuation of valproic acid.

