7.5 Laboratory Monitoring and Clinical Exam

Patients in the safety lead-in cohort (for qualifying toxicity assessment) will be seen weekly for the first 4 weeks of combination study therapy, then every 2 weeks for the next 4 weeks, and then monthly. Visits for subsequently enrolled patients are required every 2 weeks for the first 8 weeks, then monthly. Assessments to be done at each visit are as shown in the [Study Calendar](#). Serum valproic acid levels will be monitored every 2 weeks, or more frequently as clinically indicated through the end of cycle 2. After cycle 2 they will be checked as clinically indicated. Determination of steroid dose will be made at least

every 2 weeks (weekly in the safety lead-in cohort) and steroid dose may be tapered at the treating physician's discretion if the patient demonstrates a stable to improved neurologic exam.

In the event that a patient complains of abdominal pain, serum amylase and lipase will also be checked. Severe abdominal pain warrants a CT scan of the abdomen to rule out visceral perforation and pancreatitis.

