- E. If baseline history and physical exam is performed on a day other than C1D1, a brief visit to determine neurologic stability on current dose of steroids is also required on day 1 or day before.
- F. Only patients in the safety lead-in cohort.
- G. For women capable of pregnancy: pregnancy test at baseline; subsequently, review pregnancy risks and offer pregnancy test
- H. First “on-treatment” ECG is done approximately C1D8-C1D15 to evaluate acute changes relative to the study drug combination; the second is done approximately C3D1 to evaluate changes after a more chronic dosing of study drug combination.
- I. MRI or contrast-enhanced CT within 3 weeks prior to enrollment. An MRI is the preferred modality in all patients without a contraindication to MRI. Baseline and follow-up scans must be performed using the same modality.
- J. Imaging to be done to assess response every 2 months from initiation of treatment until off-study due to patient withdrawal, progression, or death. If MRI or contrast-enhanced CT shows response then repeat after 1 month to confirm response and then follow every 2 months from time of confirmatory MRI or CT. Patients with symptoms suggestive of progression may have imaging done between regularly scheduled scans, any time there is clinical concern for progressive disease. See also Section [10.4](#).
- K. See Section [7.8](#): After stopping study treatment, capture initiation of new therapy, first new progression date, and/or survival status since last observation approximately every 2 months during extended follow-up.
- L. Obtain and analyze archived tumor tissue per Section [11](#). During enrollment of the initial PDGFR α -unselected subgroup (prior to first interim analysis), archived tumor tissue must be obtained and analyzed, but analysis does not need to be performed prior to enrollment. After the first interim analysis, if the study proceeds to include only PDGFR α -positive patients, archived specimen analysis for PDGFR α will be required, and results must be known, prior to enrollment.
- M. Sodium, potassium, carbonate, chloride, glucose, calcium, BUN, creatinine.
- N. Additional assessments may be done at investigator discretion in patients with congestive heart failure, bradyarrhythmias, those on drugs known to prolong the QT interval, including Class Ia and III antiarrhythmics, and electrolyte abnormalities.
- O. ALT, AST, ALP, total bilirubin, direct bilirubin, albumin, total protein.

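### Asymptomatic grade 3-4 amylase/lipase rises count as qualifying toxicities, but the visible schedule tests for them only when symptoms arise, which mainly affects the 2-of-6 safety lead-in

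*Combined protocol and SAP*

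**What the plan says.** **The definition.** Section 6.4.2 opens: "Qualifying toxicities are defined as any of the following that are possibly, probably, or definitely related to drug therapy". It then takes in everything of grade 3 or higher except a closed list. The nearest laboratory exception is "electrolyte abnormalities that, once corrected, can be maintained with oral repletion"; hyperglycemia and blood counts at grade 3 are also excepted. Neither pancreatic enzyme is mentioned, and there is no general exception for asymptomatic laboratory findings.

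**The testing.** Section 7.5: "In the event that a patient complains of abdominal pain, serum amylase and lipase will also be checked". The Study Calendar schedules two chemistry panels. Footnote M lists "Sodium, potassium, carbonate, chloride, glucose, calcium, BUN, creatinine" and footnote O lists "ALT, AST, ALP, total bilirubin, direct bilirubin, albumin, total protein". Neither contains amylase or lipase, and no baseline value is scheduled. Table 4 in Section 7.3 calls for evaluation for pancreatitis when abdominal pain, nausea, vomiting or anorexia has no other explanation, but names no test.

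**What is expected.** Section 1.7 gives rates of 13%, 2%, 5% and 7% in four of its five cited studies. In the first, "Only 2 of the 4 patients with elevated amylase/lipase were symptomatic"; in the erlotinib combination, "The elevations of lipase were asymptomatic". Table 4 adds: "Elevations in lipase are very common in patients taking sorafenib".

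**The decision rules.** Under Sections 13.1 and 13.6.1, two or more qualifying toxicities among six evaluable patients in the first four weeks puts the protocol on hold. Section 13.6.2 then applies a sequential boundary running from 5/7 to 32/66. Section 10.1 limits both counts to cycle 1.

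**The concern.** The definition includes an event that the schedule does not look for. A grade 3 lipase rise is scored in a patient who has pain, or whose physician orders the test for another reason. The same rise is not scored in a patient who feels well and is not tested. The count then depends on symptoms and local ordering habits as well as on the regimen, and its error runs in one direction, toward too few events.

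This matters most where a single event can decide the outcome. With a threshold of two in six, one unrecorded event can turn a hold into a decision to expand.

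**Working it through.** **Inputs from the documents**
- First temozolomide-combination study: 4 patients with grade 3-4 amylase/lipase rises. The denominator is 12 + 10 + 10 = 32, so 4/32 = 12.5%, printed as 13%. Two of the 4 were asymptomatic.
- Erlotinib-combination study: 7%, all asymptomatic.
- The other two studies reporting lipase rises: 2% (1 of 43) and 5% (1 of 19), with no symptom status.
- Lead-in: hold if 2 or more of 6. Sequential rule: the printed boundary, benchmark 35%.

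**Assumptions**
- The rate *b* of all other counted events, including symptomatic enzyme rises, is not given. I use 10%, 20% and 35%.
- Asymptomatic rises are independent of the other events, and all fall in cycle 1.

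**Step 1: the plan's own boundary.** For each n from 7 to 66, take the smallest m for which m/n − 1.96·√[(m/n)(1 − m/n)/n] exceeds 0.35. At n = 7, m = 5 gives 0.714 − 0.335 = 0.380 and m = 4 gives 0.571 − 0.367 = 0.205, so the limit is 5. This Wald interval reproduces all 60 printed values.

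**Step 2: the asymptomatic rate *a*.** The two studies with symptom status give 12.5% × 50% = 6.25% and 7% × 100% = 7%. Over the full range of rates (2% to 12.5%) and asymptomatic shares (50% to 100%), *a* runs from 1% to 12.5%. The chance that at least one of six lead-in patients has such an event is 1 − (1 − a)^6, which is 32% at 6.25% and 35% at 7%.

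**Step 3: the lead-in.** Total rate p = 1 − (1 − b)(1 − a). P(hold) = 1 − (1 − p)^6 − 6p(1 − p)^5. For b = 10% and a = 6.25%, p = 1 − 0.90 × 0.9375 = 0.156 and P(hold) = 0.238.

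| b | none found (a = 0) | a = 1% | a = 6.25% | a = 7% | a = 12.5% |
|---|---|---|---|---|---|
| 10% | 0.114 | 0.132 | 0.238 | 0.254 | 0.375 |
| 20% | 0.345 | 0.364 | 0.466 | 0.480 | 0.580 |
| 35% | 0.681 | 0.693 | 0.752 | 0.760 | 0.812 |

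**Step 4: the sequential rule.** This is an exact binomial recursion over the printed boundary from n = 7 to 44 (the plan's expected sample size), with the first six patients counted and any lead-in hold ignored.

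| b | a = 0 | a = 6.25% | a = 7% |
|---|---|---|---|
| 20% | 0.007 | 0.022 | 0.025 |
| 35% | 0.139 | 0.251 | 0.268 |

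The shift is under 2 points at b = 20% and about 11 to 13 points at b = 35%.

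**The case against.** The strongest defense is that symptom-driven testing is deliberate. Table 4 warns against diagnosing pancreatitis from laboratory values alone, Table 1 treats laboratory abnormalities without clinical significance separately, and Section 7.5 adds abdominal CT for severe pain. Symptomatic pancreatic events are therefore looked for. This stands as an account of patient management. It does not settle the count: the Table 1 row governs sorafenib dosing, and nothing in Section 6.4.2 removes asymptomatic enzyme rises.

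Several stronger readings are tempting but not supported:

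- *The counts miss amylase/lipase toxicity altogether.* Rises with abdominal pain are tested, so only the asymptomatic part is exposed: 2 of 32 in the first study, not 4 of 32.
- *Abdominal pain is the only trigger.* It is the only explicit one. Table 4 adds a work-up for nausea, vomiting or anorexia, and Section 9 is redacted, so an instruction there cannot be excluded.
- *At least half of these rises are known to be silent.* Symptom status comes from two studies, one with four cases; one of the two symptomatic cases there had gallstones as the likely cause.
- *The sequential rule also turns on one or two events.* Its boundary starts at 5 of 7, and Section 13.6.2 describes it as looser than the lead-in.
- *A pancreatic interaction signal is being hidden.* The documents show no such signal, and Section 1.7 expects no major overlapping toxicities.

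The missing baseline is also a lesser matter, since a possible relation to treatment is enough for an event to count.

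**Conclusion.** The mismatch is real on the visible text: the definition counts asymptomatic grade 3-4 amylase/lipase rises, and no visible scheduled test would find them. At an asymptomatic rate of about 6%, finding them all would raise the chance of a lead-in hold by about 12 points at base rates of 10% or 20%, and by about 7 points at 35%. Over the full range of *a*, the rise is roughly 1 to 26 points. The sequential rule is little affected unless the base rate is already near 35%.

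These sizes are illustrative. The base rates are assumptions, the cited studies combined sorafenib with other agents, and their rates are not limited to cycle 1, so the true effect could be smaller. It could also be larger, because the 13% counts only patients whose sorafenib was modified or stopped. The figures do not show that the lead-in would reach a wrong decision, only that its result can depend on who is tested.

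**What to change.** Reconcile Section 6.4.2, Section 7.5 and the Study Calendar before the first lead-in decision, so that every patient has the same chance of being counted. There are two consistent ways to do it:

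- Asymptomatic enzyme rises count, and are ascertained in all patients at baseline and at cycle-1 blood draws already scheduled. The cost is an added assay on existing samples and a few more counted events (44 × 6.25% ≈ 3 at the expected sample size).
- Asymptomatic enzyme rises do not count, and Section 6.4.2 lists them as an exception, so that an incidental result is not scored either. The cost is one line of text.

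The choice is a clinical one for the sponsor. If the redacted Section 9 already contains a monitoring instruction, a cross-reference from Sections 6.4.2 and 7.5 and the calendar would close the gap.
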